Aim 2: To determine whether financial incentives will increase the duration of exercise performed by American Indian youth at a community fitness center. Participants who complete Aim 1 will be re-randomized to one of two groups for a second 16-week period of exercise: Control (\$4/session, up to 3 sessions/week), or Incentive (\$4, \$7, or \$10 for 20-, 40-, or 60- minute sessions, respectively, up to 3 sessions and \$30/week). Transportation and professional supervision will remain the same as in Aim 1. A secondary goal is to assess the association between exercise duration and changes in diabetes-related risk factors.

Aim 3: To determine whether ongoing incentives are required for maintenance of fitness center utilization established with financial incentives. Participants who complete Aim 2 will enter a third 16-week exercise period with diminished monetary incentives. Each person will be re-randomized to one of two incentive structures: a) Ramp-down, with financial incentives diminishing to zero by 8 weeks, or b) Raffle, with monetary prizes awarded through a drawing in which chances of winning are dependent on frequency and duration of exercise. We hypothesize that exercise behavior will remain above zero even after financial incentives decline and that the Raffle approach will reinforce the best exercise behavior maintenance. Clinical diabetes risk outcomes will be measured as in Aims 1 and 2.

Aim 4: To measure the impact of physical activity and physical fitness on circulating biomarkers of metabolic disease risk. Normal weight American Indian youth with either low physical activity and fitness or high physical activity and fitness will be studied on a single occasion. Serum/plasma concentrations of lipids, amino acids, and related markers of inflammation, and oxidative and vascular stress will be compared among the normal weight participants and the overweight/obese youth enrolled in Aims 1-3.

This study will clarify how specific incentive structures can be used to promote exercise in a population of adolescents at exceptionally high risk for diabetes and cardiometabolic disease. The study will also provide needed insight on the volume of exercise needed to elicit changes in clinical outcomes. These results will be used to develop better lifestyle intervention strategies for American Indian youth.

[figure not shown]
RESEARCH STRATEGY: APPROACH

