Design: Specific Aims 1-3 will follow a single prospective, randomized trial design, with 105 participants

enrolled and 80-90 entering the exercise program (**Fig 1**). The individual Aims are distinguished by sequential study phases and varying incentive structures (**Fig 2 and 3**). Aim 4 is a cross-sectional comparison between overweight/obese participants entering the main trial and two groups of normal weight youth (up to 40 participants per group) with either low physical activity and fitness or high physical activity and fitness (up to 40 participants per group).

Participants: Male and female American Indian youth 11-21 years old will be recruited from the Choctaw Health Service Area of SE Oklahoma. For the primary exercise incentives study, the eligibility criteria include BMI ≥85th percentile for age- and sexspecific norms based on growth charts from the Centers for Disease Control, maturation level ≥Tanner Stage 2 for breasts (girls) or genitalia (boys), family history of T2D, and recent history of low physical activity. Low physical activity, defined as attaining < 30 minutes of structured moderate-to-vigorous intensity exercise on \leq 3 days/week over the preceding 3 months, will be confirmed through guestionnaires and objective monitoring as described below. For both normal weight comparison groups in Aim 4, eligibility will include BMI greater than 20th and less than 85th percentile, maturation level ≥Tanner Stage 2 for breasts (girls) or genitalia (boys), and recent history of either a) low physical activity (same as the overweight/obese group) or, b) high physical activity (>30 minutes of structured moderate-to-vigorous intensity exercise on >3 days/week over the preceding 3 months. T2D family history will be recorded but will not be an inclusion criterion for the normal weight groups. Fitness level and physical activity will be determined through testing, described below. Additional enrollment and retention eligibility criteria are: lack of diabetes or other potentially confounding metabolic disorders, able to safely exercise, willingness to complete the testing and participation schedule, and not on medications known to impact the stated outcomes. A medical history and physical exam will be performed to assure suitability for the study during the initial screening.

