Fitness testing: Bicycle ergometer tests with increasing workloads will be used to measure maximal aerobic work output, peak rate of oxygen consumption (VO₂peak) and heart rate, and the workload corresponding to a heart rate of 170 beats/min (48, 77). Submaximal stages will be used to establish relationships among heart rate and power and used to assess work economy. Continuous measurements of expired gases will be performed with a facemask and metabolic measurement cart and heart rate with Polar heart rate monitors. For normal weight participants, the cut point for fitness level (low versus high) will be a VO₂peak of 46 ml/kg/min for boys and 37 ml/kg/min for girls. This threshold was identified as a marker of elevated metabolic risk, based on a composite of standard clinical outcomes such as blood pressure, glucose, lipids, and waist circumference, in a cohort of more than 2,000 adolescents (age ~15 y), who performed a standard bicycle fitness test (4).

Physical activity assessment: Free-living daily ambulatory activity will be measured with accelerometers worn on the waist (Fitbit Zip, Fitbit Inc.) throughout the day, recording data each minute for 7 days. Data analysis includes total step count and activity patterns based on step rates. We have recently completed validation and reliability assessments of these monitors in our laboratory have found very high levels of agreement with other waist or ankle-worn accelerometers.

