Data analyses: Since group assignments will be balanced for age and sex, the groups are expected to be similar at baseline. Additional comparisons will be performed to identify demographic or other variables on which the groups might differ (e.g., weight loss) that could affect the primary outcomes. Subsequent analyses will adjust for these potentially confounding variables. Regression models, which adjust for modifier (or confounding) variables identified in initial data exploration, will compare between-group differences in the primary outcomes. Since we anticipate that the number of fitness center visits, which is the primary outcome in Aim 1, will follow a Poisson distribution typical of counts, we will explore a multivariable Poisson regression model to analyze that aim. To assess Aim 2, a more conventional regression model will analyze the primary outcome, which is the total time that participants engage in exercise. The effects of exercise training on secondary outcomes will be analyzed similarly, using multiple linear regression. Analysis of Aim 3 will also utilize multivariate modeling to determine which factors, including exercise group assignment, best explain the change in exercise volume and clinical outcomes over the final phase of the study. Residuals generated from regression models will be inspected for normality and data will be log-transformed or subjected to nonparametric testing as appropriate. Aim 4 is a cross-sectional study design so the main effects of physical activity (high versus low), fitness (high versus low) and body size (normal weight versus overweight/obese) on biomarkers of metabolic disease risk will be initially determined using an analysis of variance approach, with Bonferroni tests to make pairwise comparisons between groups. A multivariate modeling approach, similar to that used in Aims 1-3, will be used to identify the best sets of predictor variables for specific biomarkers. A P value <0.05 will be considered statistically significant.

BIBLIOGRAPHY

- 2. Adams SH. Emerging perspectives on essential amino acid metabolism in obesity and the insulinresistant state. *Adv Nutr* 2: 445-456, 2011.

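### Aim 4's ANOVA promises separate activity and fitness effects, but the three groups as described allow only their joint effect to be estimated

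*Combined protocol and SAP*

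**What the plan says.** The Data analyses section says that an initial ANOVA will determine "the main effects of physical activity (high versus low), fitness (high versus low) and body size (normal weight versus overweight/obese) on biomarkers". Bonferroni pairwise comparisons between groups follow, and then a multivariate model to find the best predictors of each biomarker.

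The groups are described elsewhere:

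- **Specific Aims, Aim 4:** "Normal weight American Indian youth with either low physical activity and fitness or high physical activity and fitness" are studied once and compared with the overweight/obese youth of Aims 1-3.
- **Design:** the comparison uses "two groups of normal weight youth (up to 40 participants per group) with either low physical activity and fitness" or with both high.
- **Participants, overweight/obese youth:** eligibility includes "family history of T2D, and recent history of low physical activity".
- **Participants, normal weight youth:** the criteria name activity history but no fitness level. The section adds: "Fitness level and physical activity will be determined through testing, described below". On family history: "T2D family history will be recorded but will not be an inclusion criterion for the normal weight groups".
- **Fitness testing:** "For normal weight participants, the cut point for fitness level (low versus high) will be a" VO2peak of 46 ml/kg/min in boys and 37 in girls. No cut point is given for overweight/obese youth, although their aerobic fitness is measured at baseline.

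No rule covers discordant normal weight youth, meaning those high on one of activity and fitness and low on the other.

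**The concern.** Separate main effects of two factors need participants in whom the factors differ. In both normal weight groups as described, activity and fitness rise or fall together. The overweight/obese group adds no variation in activity, and none in fitness unless some of its members are classed as fit. Software given this model would drop one term or place the joint effect under one label. A published activity effect or fitness effect would then be the sum of the two, although Aim 4 exists to measure the impact of both.

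A second imbalance affects the body-size comparison. Family history of type 2 diabetes is an entry criterion for overweight/obese youth only, so an unadjusted contrast carries part of any effect that family history has on a biomarker.

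**Working it through.** The documents give no power, effect size or SD for Aim 4, so there is no planned figure to reproduce. The check is of estimability.

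**Inputs.** 40 per normal weight group (the stated maximum) and 90 overweight/obese (upper end of the 80-90 entering the exercise program). Residual SD is set to 1. Power of 80%, two-sided 0.05 and all shares below are assumptions.

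**1. Groups as described, overweight/obese coded low-fit**

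| Group | Intercept | Activity (A) | Fitness (F) | Overweight (B) |
|---|---|---|---|---|
| Normal weight low/low | 1 | 0 | 0 | 0 |
| Normal weight high/high | 1 | 1 | 1 | 0 |
| Overweight/obese | 1 | 0 | 0 | 1 |

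The A and F columns are identical, so the rank is 3 for 4 parameters. Neither A nor F is estimable. What remains is:

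- joint effect A + F: SE = sqrt(1/40 + 1/40) = 0.224 SD
- body size B: SE = sqrt(1/40 + 1/90) = 0.190 SD (0.194 with 80 overweight/obese youth, 0.186 with 105)

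Detectable differences:

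- Uncorrected, multiplier 1.960 + 0.842 = 2.80: 0.63 SD joint, 0.53 SD body size.
- Bonferroni for three pairwise tests, multiplier 2.394 + 0.842 = 3.236: 0.72 SD and 0.61 SD.

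**2. Overweight/obese left without a fitness class.** A model containing fitness can then use only normal weight youth: rank 2 for 3 parameters (intercept, A, F). Again only A + F is estimable.

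**3. Discordant normal weight youth kept.** Suppose k of 40 in each group are discordant. All four activity-by-fitness cells are then filled among normal weight youth, so averaged A and F effects are estimable there even with an interaction in the model. For each effect:

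SE = sqrt[(1/(40-k) + 1/k + 1/(40-k) + 1/k) / 4]

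- k = 4 (10%): sqrt(0.5556/4) = 0.373 SD, detectable 1.04 SD uncorrected
- k = 8 (20%): sqrt(0.3125/4) = 0.280 SD, detectable 0.78 SD uncorrected

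**4. Some overweight/obese youth classed as fit, normal weight groups as described.** F is estimated only within overweight/obese youth, and A is the joint effect minus F.

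- 9 of 90 fit (10%): SE(F) = sqrt(1/9 + 1/81) = 0.351; SE(A) = sqrt(0.05 + 0.1235) = 0.416
- 18 of 90 fit (20%): SE(F) = sqrt(1/18 + 1/72) = 0.264; SE(A) = sqrt(0.05 + 0.0694) = 0.346

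If the fitness effect is larger by d in overweight/obese youth, the activity estimate becomes (A + F) - (F + d) = A - d, so it is wrong by the full d. Adding a fitness-by-body-size term gives rank 4 for 5 parameters, and A and F are inestimable again.

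**5. Family history in the body-size contrast.** All overweight/obese youth have it. Let p be the share in each normal weight group (not given in the documents). The unadjusted contrast carries (1 - p) of any family-history effect. After adjustment with a common effect, SE = sqrt[1/40 + 1/90 + (1 - p)/(80p)].

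| p | Share of effect carried | Adjusted SE (SD) |
|---|---|---|
| 0.10 | 0.90 | 0.39 |
| 0.25 | 0.75 | 0.27 |
| 0.50 | 0.50 | 0.22 |
| 0.75 | 0.25 | 0.20 |
| 0.90 | 0.10 | 0.19 |

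**The case against.** The best defence is that the aliasing depends on a reading the plan leaves open. Normal weight eligibility rests on activity history alone and fitness is tested afterwards, so discordant youth may well be enrolled, and nothing excludes them. If they are kept and occur in both groups, the separate effects are estimable among normal weight youth. This stands, and it is why the point is conditional. The Specific Aims and Design still describe groups that pair the two factors, and no rule says what happens to youth who do not fit.

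A second defence is that much of the remedy is already planned. The ANOVA is only the initial step. Pairwise comparisons among three groups already contain both interpretable contrasts, and the later model could separate activity from fitness using measured VO2peak and step counts. This stands in part: the form of those predictors is not specified, and a later model does not repair the stated ANOVA.

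On family history, the Data analyses section says generally that variables on which groups differ will be adjusted for. That may reach the later Aim 4 model, but it is not stated for the ANOVA or its pairwise tests.

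A reader might go further and infer that Aim 4 can never separate activity from fitness, or that every separate estimate rests on additivity. The documents do not support either. Discordance in both directions removes the need for additivity within normal weight youth, and the second route needs only a fitness effect common to both body sizes.

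**Conclusion.** The point holds in conditional form. With the three groups as described, and overweight/obese youth coded low-fit or left unclassified, the planned ANOVA cannot give separate activity and fitness effects. That result follows from the group definitions and needs no assumed SD or effect size. Coded low-fit, the design still supports the joint effect and the body-size difference, with detectable differences of about 0.72 and 0.61 SD after Bonferroni for three tests at the assumed numbers.

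The routes to separate effects exist but are imprecise: 0.78-1.04 SD detectable, uncorrected, at an assumed 20% or 10% discordance. The fit-overweight route also carries an assumption that its own data cannot test.

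The family-history imbalance is built in by eligibility, but its size is unknown, because neither the normal weight share nor the effect is given.

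This should be fixed before analysis. It does not touch the randomised comparisons in Aims 1-3, and a reader should not extend it to them.

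**What to change.** In Data analyses, for the groups as described, replace the three-main-effect ANOVA with a three-group model adjusted for age and sex, keeping all three Bonferroni pairwise comparisons:

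1. Normal weight high/high minus low/low, labelled the joint activity-and-fitness effect.
2. Overweight/obese minus normal weight low/low, labelled the body-size difference among low-activity youth. Report it with and without adjustment for recorded family history, noting that adjustment assumes the same family-history effect at both body sizes.
3. Normal weight high/high versus overweight/obese, reported as a comparison in which body size, activity and possibly fitness all differ.

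State whether discordant normal weight youth are excluded or analysed, and whether the fitness cut point applies to overweight/obese youth. Report separate activity and fitness effects only from the planned multivariable model with continuous VO2peak and step counts, or from a categorical model if discordant normal weight youth are kept under the stated rule.

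**Cost.** No new data: the measurements are already planned and family history is recorded. Separate categorical effects are no longer claimed for the groups as described. Adjusting contrast 2 for family history moves its SE from 0.19 SD to between 0.19 and 0.39 SD, for assumed normal weight shares of 90% down to 10%.

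### Aim 4's plain Bonferroni pairwise tests are valid but give away some power that a step-down version would recover at the same 5% error rate per biomarker

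*Combined protocol and SAP*

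**What the plan says.** The Design paragraph describes the comparison: "Aim 4 is a cross-sectional comparison between overweight/obese participants entering the main trial and two groups of normal weight youth". The normal weight groups, one with low and one with high activity and fitness, are capped at "up to 40 participants per group". The overweight/obese group comes from the main trial, which has 105 "enrolled and 80-90 entering the exercise program".

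The Data analyses section says that the main effects of activity, fitness and body size on the biomarkers "will be initially determined using an analysis of variance approach", "with Bonferroni tests to make pairwise comparisons between groups". The general criterion is "A P value <0.05 will be considered statistically significant". The section does not name a step-down version, say why plain Bonferroni was chosen, define the family of tests or state sidedness. The documents give no effect size, SD or power calculation for Aim 4.

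**The concern.** Plain Bonferroni charges every pair the full threefold penalty even after one pair has been shown to differ. With three means that is more than is needed. If one pair truly differs, at most one of the other two can be equal, so there is no longer a family of three to protect.

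The pair most exposed is normal weight low versus high. It is the only pair that varies activity and fitness without also varying body size, and it compares the two smallest groups. A step-down method could recover power there without new data and without raising the error rate within a biomarker.

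**Working it through.** The plan has no Aim 4 power figure to reproduce, so the check compares procedures.

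**Inputs.** From the documents: three groups, up to 40 in each normal weight group, 80 to 90 overweight/obese, alpha 0.05. Assumed: two-sided pooled-variance t tests, equal SDs, full normal weight groups, and the effect sizes below.

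**Thresholds for the ordered P values, three pairs.**
- Bonferroni: 0.05/3 = 0.0167 for each.
- Holm: 0.05/3 = 0.0167, then 0.05/2 = 0.025, then 0.05, stopping at the first failure.
- Shaffer: smallest at 0.0167; if it is rejected, the other two at 0.05 each.

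The first threshold is the same in all three, so the chance of at least one rejection is identical. Later thresholds are never stricter than 0.0167, so no Bonferroni rejection can be lost.

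**Why Shaffer's version holds 5%.** Among three means, the number of truly equal pairs can be 3, 1 or 0, never 2. With 3, any error needs the smallest P to be at or below 0.05/3, which has probability at most 5%. With 1, an error needs that pair's own P to be at or below 0.05, again at most 5%.

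**What the threshold is worth for one test.** Power is about Φ(d/SE − z), with SE = √(1/n₁ + 1/n₂) in SD units.
- 40 versus 40, d = 0.5: SE = 0.2236 and d/SE = 2.236. Power is Φ(2.236 − 2.394) = 43.7% at 0.0167, Φ(2.236 − 2.241) = 49.8% at 0.025 and Φ(2.236 − 1.960) = 60.9% at 0.05.
- 40 versus 85, d = 0.5: 58.5%, 64.3% and 74.1%.

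The gain over the first figure is realised only when another pair has already been rejected, so simulation is needed.

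**Simulated power for normal weight low versus high.** The first three rows use 40/40/80 and the last three 40/40/85. Figures are rounded, and repeat runs differ by up to about a point.

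| Overweight/obese mean | Low vs high, SD | Bonferroni | Holm | Shaffer |
|---|---|---|---|---|
| 0.5 SD beyond low | 0.4 | 27% | 38% | 43% |
| 0.5 SD beyond low | 0.5 | 43% | 57% | 60% |
| 0.5 SD beyond low | 0.6 | 61% | 74% | 76% |
| equal to low | 0.5 | 43% | 47% | 53% |
| midway between low and high | 0.5 | 43% | 44% | 46% |
| 0.2 SD beyond low | 0.2 | 7% | 8% | 12% |

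The Holm gain runs from 44 − 43 = 1 to 57 − 43 = 14 points. The Shaffer gain runs from 46 − 43 = 3 to 60 − 43 = 17 points. The gain is large when the overweight/obese versus high pair is almost always rejected first. It is small when low versus high is itself the widest pair.

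**Other results at 40/40/85.** With means 0.5 SD apart, power to find all three pairs is 15.7% with Bonferroni and 36.4% with Holm. Error within a biomarker with all means equal is 4.3% for each method. With one equal pair it is 1.7% for Bonferroni and 2.9% for Holm (overweight/obese 0.5 SD from two equal groups); for Shaffer it is 4.8-4.9% at moderate separation and 5.0% at extreme separation. No simulated Bonferroni rejection was lost.

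**The case against.** The strongest reply is that the same sentence tests main effects by ANOVA first, with no stated Bonferroni penalty. Overweight/obese participants are all low-activity by eligibility. In an additive model with activity and body size over the three groups, the activity effect is therefore exactly normal weight low versus high, and the body-size effect is exactly overweight/obese versus normal weight low. Simulated data gave identical P values both ways. At 0.5 SD those tests have about 60% and 74% power, the same as the Shaffer result. A reader might infer from the Bonferroni wording that real activity or fitness effects will be missed. The documents do not support that, because on this reading the key contrast is already tested at 0.05. The reading is not certain: fitness is listed as a further factor and the model is not written out. The pairwise step still loses power as written.

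Three further replies have some force:
- The larger gains assume that the overweight/obese group lies well beyond normal weight low. Nothing in the documents says so, which is why the full range is given above.
- The three two-level factors could produce more than three cells. Shaffer's 0.05 rule would then not apply, but Holm's advantage over Bonferroni would remain.
- Aim 4 covers many biomarkers with no primary one named, so loosening the only stated correction may seem the wrong priority. But step-down testing does not raise the guaranteed 5% limit within a biomarker, and neither method as described controls error across biomarkers.

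A one-way three-group F test as a gate, followed by unadjusted pairwise tests at 0.05, would also hold 5% (simulated 4.8-5.0%). With means 0.5 SD apart its average power per pair is 78.0%, against 75.5% for Holm. The plan lists main effects and not one three-group factor, so that gate would have to be specified.

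**Conclusion.** The point stands as a modest efficiency improvement and not as an error in the plan. Plain Bonferroni is valid. Within each biomarker, Holm or (for exactly three groups) Shaffer keeps the 5% rate and never rejects less.

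For normal weight low versus high, the gain is about 1 to 14 points with Holm and 3 to 17 with Shaffer. This rests on full normal weight groups of 40, 80 to 85 overweight/obese participants, equal SDs and assumed effects. A reader might take the top of the range as typical; it holds only where the overweight/obese mean lies well beyond normal weight low. The benefit is limited to the follow-up pairwise tests and does not touch the randomised comparisons in Aims 1-3.

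**What to change.** In the Aim 4 sentence of the Data analyses section, replace the Bonferroni tests with Holm-adjusted pairwise tests within each biomarker. If exactly the three groups in the Design paragraph are compared, Shaffer's version may be named instead: smallest P value against 0.0167 and, if significant, the other two against 0.05 each. State which groups are compared and that the family is the set of pairs within one biomarker. Any control across biomarkers should be specified separately and can be applied on top.

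The cost is one sentence of analysis wording, with no new data or procedures. The small downside is that step-down tests have no simple matching simultaneous confidence intervals. Bonferroni intervals can still be shown beside the adjusted P values, with a note that they may be wider than the tests imply.

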After completing Aim 1 and the associated post-test, all participants who completed an average of \geq 1 exercise session per week will be eligible to continue on to Aim 2. The only difference between Aims 1 and 2 will be the financial incentive scheme; the overall exercise goals, and provision of transportation and professional oversight will remain the same. Similarly, after completing Aim 2 and the associated post-test, all participants who have averaged \geq 1 exercise session per week in Aim 2 will be eligible to continue on to Aim 3. No changes will be made to the exercise goals or availability of transportation and facilities in Aim 3.

To allow for potential schedule conflicts and missed sessions (e.g., illness, travel) participants will be allowed to "catch-up" by performing up to 3 extra sessions within the 3 weeks following a week with less than 3 sessions. Thus, if an entire week is missed due to illness, 12 sessions for payment can be completed over the next 3 weeks instead of the targeted 9 sessions. Additionally, participants will not be discouraged from performing more than the targeted exercise volume of 3 days per week of 60 minutes per session. Exercise beyond this target that is performed at school, at home or at the Wellness Centers is acceptable, since the goal of this program is to foster increased physical activity. Participants will be instructed to include such extra physical activity in their exercise log book, though they will not receive payment for days or time beyond the structured incentive program. This information will be used as part of the data analysis plan if applicable.

Post-training testing: After each of the 16-week exercise phases in Aims 1, 2, and 3, the clinical outcome tests performed at the baseline will be repeated. Staff that supervise exercise sessions will not be blinded to group assignment, but most other staff, including nurses and chemistry lab staff, will not know group assignments, so the potential for bias is expected to be low. The fasting blood sample will be acquired 2 days (38-48 hours) after the last exercise session in order to assess exercise adaptations that are distinct from the residual effects of the most recent training session. The exercise fitness and body composition tests will also be repeated at the end of each study phase.

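### Aims 3 and 4 search for the best predictors under a single uncorrected P<0.05, with no validation or optimism correction, so significance and fit will be overstated

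*Combined protocol and SAP*

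**What the plan says.** All the relevant text is in the Data analyses paragraph.

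- Aim 3: multivariate modelling is to be used "to determine which factors, including exercise group assignment, best explain the change in exercise volume and clinical outcomes" over the final phase. The randomised group is one factor among those searched.
- Aim 4: after an analysis of variance "with Bonferroni tests to make pairwise comparisons between groups", a modelling approach like that of Aims 1-3 "will be used to identify the best sets of predictor variables for specific biomarkers".
- Adjustment variables: the between-group regressions are ones "which adjust for modifier (or confounding) variables identified in initial data exploration", so the same data choose the covariates.
- Threshold: "A P value <0.05 will be considered statistically significant". This closes the paragraph, and no analysis is exempted from it.

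For the Aim 3 and Aim 4 searches the paragraph gives no candidate list, selection procedure, shrinkage, internal validation or multiplicity control. It does not call them exploratory.

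**The concern.** When the same data choose the predictors and then test them, ordinary P values and intervals no longer have their nominal meaning, and the R2 of the chosen model is too high. A model with many candidates also has a plain multiplicity problem before any selection takes place. The Bonferroni step in Aim 4 addresses neither, because it applies only to pairwise comparisons between groups.

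Two things are at stake. First, the Specific Aims say the results will feed into later lifestyle interventions for this population, so chance predictors with inflated fit could steer that work. Second, Aim 3 states a directional hypothesis favouring the Raffle. The plan's only description of the Aim 3 analysis places that randomised contrast inside a search, so its estimate could depend on which other factors are selected.

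**Working it through.** The documents state no error rate, candidate count or R2 for these models, so there is no planned figure to reproduce. The check asks what the plan would yield if no candidate were related to the outcome.

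**Inputs from the documents**
- Threshold 0.05 (Data analyses).
- Aim 3 size: 105 "enrolled and 80-90 entering the exercise program" (Design). Entry to Aim 3 then requires an average of at least one session a week in both earlier phases (Exercise training), so 80-90 is an upper bound.
- Aim 4 size: "two groups of normal weight youth (up to 40 participants per group"), so up to 2 × 40 = 80, plus the overweight/obese entrants. Taking 85 as the middle of 80-90 gives 80 + 85 = 165.
- Biomarkers named under Plasma/serum analysis: 4 lipids + 8 pro-inflammatory or vascular markers + 4 amino acids or metabolites = 16, besides HbA1c and an acyl CoA panel.

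**Assumptions**
- n = 60 or 85 for Aim 3 and 165 for Aim 4.
- k = 8, 12 or 16 candidates, pairwise correlation 0.3.
- Backward selection by AIC, then P<0.05 on the same data.
- All true effects zero.

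**Step 1: multiplicity alone.** With k independent tests, P(at least one P<0.05) = 1 − 0.95^k.

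**Step 2: simulation.** Share of null data sets with at least one P<0.05 predictor in one model, as a range over n = 60, 85 and 165:

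| k | 1 − 0.95^k | Full model, no selection | Backward AIC, then P<0.05 |
|---|---|---|---|
| 8 | 34% | about 28-33% | about 40-46% |
| 12 | 46% | about 42-46% | about 58-66% |
| 16 | 56% | about 54-56% | about 72-80% |

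Selection thus adds roughly 8-26 points. With 600 data sets per cell the standard error near 50% is √(0.5 × 0.5/600) = 0.02, so single cells move by about 4 points between runs. A repeat with 2,000 data sets per cell gave 30-32%, 41-43% and 48-53% for the full model and 40-44%, 57-62% and 69-75% after AIC. The pattern is the same, with the k = 16 figures a few points lower.

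**Step 3: another selection rule.** With forward entry at P<0.05 (n = 50, 85 or 165; correlation 0 or 0.3) the share was 21-24% for k = 5, 34-40% for k = 10, 41-55% for k = 14 and 54-66% for k = 20. By the Step 1 formula the chance passes one half between k = 13 (0.487) and k = 14 (0.512).

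**Step 4: fit.** The true R2 is 0. Mean apparent R2 after backward AIC was about 0.03-0.06 at n = 165 and 0.06-0.19 at n = 60-85. With forward P<0.05 entry, expected R2 in new data was negative in every scenario (about −0.04 to −0.23). An unselected full model has expected raw R2 of k/(n − 1): 16/59 = 0.27 at n = 60 with k = 16, and 8/84 = 0.095 at n = 85 with k = 8. These exceed the values after selection in the same cells (0.19 and 0.06).

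**Step 5: across the biomarker panel.** If tests were independent, one null candidate for each of 16 biomarkers gives 1 − 0.95^16 = 0.56, and two give 1 − 0.95^32 = 0.81. Correlated biomarkers would lower these.

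**The case against.** The strongest reply is that the size depends on choices the plan never makes. It states a modelling goal, not an algorithm. It gives no candidate count, and it does not say outright that selected terms will be tested after selection; that follows from the blanket threshold. This stands, and it is why the figures are conditional. It does not remove the point, because nothing in the plan exempts these models from P<0.05.

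A reader might infer that chance predictors will usually be declared significant. The documents do not support this for a single model: with 5-10 candidates the rate is about 21-52%, depending on the rule. More candidates are plausible. The protocol measures at least 17 suitable variables: age, sex, Tanner stage, BMI, diabetes family history, waist, hip, fat, lean tissue, blood pressure, HOMA-IR, VO2peak, maximal work output, workload at 170 beats/min, work economy, step count and activity pattern. It does not say how many would enter.

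A reader might also infer that much of the resulting list would be noise. That was not estimated. The simulation gives the chance of at least one false predictor when all are false. Real associations with adiposity, fitness and activity are likely here, and the protocol itself describes the pro-inflammatory markers as linked to obesity and insulin resistance.

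Nor should the whole rate be blamed on selection. Most of it arises in a full model with no selection, so merely pre-listing a full model would not cure the problem and would raise raw R2.

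Finally, the scope is limited. The Aim 1 and Aim 2 primary group comparisons are described separately, and the Aim 4 analysis of variance with its Bonferroni tests is unaffected.

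**Conclusion.** The concern holds in a conditional form. For the Aim 3 and Aim 4 predictor searches, the chance of at least one false P<0.05 predictor is well above 5% in every scenario examined. It is more likely than not with about 12-14 or more candidates in one model (about 12 under AIC, about 14 if candidates are independent, and more under P-value entry if they are correlated), or across the biomarker panel if its tests are roughly independent. Fit is overstated in all scenarios, most at the smaller Aim 3 sample sizes. These are global-null, worst-case rates resting on an assumed candidate count, selection rule, correlation and sample size after attrition. The stronger statements, that false findings are the usual result or make up most of the list, are not established. This should be changed, but it concerns the Aim 3 and follow-on Aim 4 modelling rather than the Aim 1 or Aim 2 primary analyses.

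**What to change.** 1. **Aim 3 randomised contrast.** Test Ramp-down versus Raffle in a pre-specified model in which the group term is always kept, separate from any search.
2. **Predictor searches in Aims 3 and 4.** List the candidates in advance. Use a penalised model or a stated selection procedure, and repeat the whole procedure in bootstrap samples. Report inclusion frequencies and optimism-corrected R2. Attach no P<0.05 claims to selected predictors, and label the results exploratory.
3. **If a pre-listed full model is preferred.** It is acceptable only with multiplicity control and optimism-corrected R2. A Bonferroni threshold of 0.05/k controls error within one model only (for forward entry the simulated chance of any false predictor was 0.04-0.06 for k = 5 to 20); control across biomarkers needs a further step.

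The cost is a little more programming and fewer predictors that can be reported as significant. No new data or participants are needed.
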